5.3 LIFESTYLE CONSIDERATIONS

During this study, participants will be asked to partake in the lifestyle intervention as outlined in detail in the study protocol. They are to refrain from starting any of the following treatments while enrolled in the study:

- Any new lifestyle or non-pharmacologic therapy for weight loss
- Any new exercise program
- Any medication or supplement for weight loss or appetite control

Participants are asked to let the study team know about any new lifestyle or non-pharmacologic therapies started for other reasons, e.g. physical therapy for knee pain or osteoarthritis. Likewise, participants should tell the study team about any new medications that might affect weight (e.g. metformin or some SSRIs, etc.)

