6.3 MEASURES TO MINIMIZE BIAS: RANDOMIZATION AND BLINDING

Participants in this trial will be randomized to either the intervention arm (tailored physical activity and nutritional counseling) or a wait-list control arm that receives usual care for 6 months, after which they will receive the intervention (for 6 months). Neither participants nor interventionists are blinded to study arm.

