7.1 DISCONTINUATION OF STUDY INTERVENTION/EXPERIMENTAL MANIPULATION

Discontinuation from study intervention does not mean discontinuation from the study, and remaining study procedures should be completed as indicated by the study protocol. If a clinically significant finding is identified (including, but not limited to changes from baseline) after enrollment, the investigator or qualified designee will determine if any change in participant management is needed. Any new clinically relevant finding will be reported as an adverse event (AE).

The minimum data to be collected at the time of study intervention discontinuation will include the following:

- Weight and anthropometrics, laboratory studies, HRQOL and VCTE if possible.
- Download of all available Fitbit data

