7.2 PARTICIPANT DISCONTINUATION/WITHDRAWAL FROM THE STUDY

Participants are free to withdraw from participation in the study at any time upon request. An investigator may discontinue or withdraw a participant from the study for the following reasons:

- Pregnancy
- If any clinical adverse event (AE), laboratory abnormality, or other medical condition or situation occurs such that continued participation in the study would not be in the best interest of the participant
- Disease progression which requires discontinuation of the study intervention

- If the participant meets an exclusion criterion (either newly developed or not previously recognized) that precludes further study participation
- Participant unable to receive study intervention for 30 days/4 weeks
- Start of new therapy/program that is not allowed while enrolled in this study

The reason for participant discontinuation or withdrawal from the study will be recorded on the appropriate CRF. Subjects who sign the informed consent form and are randomized but do not receive the study intervention may be replaced. Subjects who sign the informed consent form, and are randomized and receive the study intervention, and subsequently withdraw, or are withdrawn or discontinued from the study, will not be replaced.

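### Starting a barred therapy or programme is a ground for withdrawal from the study itself, so the 6-month CAP can be lost after randomisation for a reason plausibly linked to outcome

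*Combined protocol and SAP*

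**What the plan says.** Section 5.3 addresses participants in both arms for as long as they are enrolled: "They are to refrain from starting any of the following treatments while enrolled in the study". The list includes "Any new lifestyle or non-pharmacologic therapy for weight loss" and "Any new exercise program", and also weight-loss or appetite medication and supplements.

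Section 7.2 opens its list of grounds with "An investigator may discontinue or withdraw a participant from the study for the following reasons". One ground is "Start of new therapy/program that is not allowed while enrolled in this study". A separate ground covers a participant who comes to meet an exclusion criterion that precludes further participation. Exclusion 6 in Section 5.2 concerns planned weight-reduction procedures and regimented programmes; exclusion 7 concerns current weight-reduction drugs or supplements. For a withdrawal, Section 7.2 asks only that the reason go on the CRF.

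Section 7.1 is more protective. It separates stopping the intervention from leaving the study, says the remaining procedures should be completed, and adds: "The minimum data to be collected at the time of study intervention discontinuation will include the following". The items that follow include VCTE if possible.

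On allocation, Section 6.3 states: "Neither participants nor interventionists are blinded to study arm". The primary endpoint in Section 3 is a reduction of at least 5% in CAP at 6 months. Section 9.3.2 specifies a modified intention-to-treat analysis and an analysis of those with complete data, and gives no rule for filling in a missing CAP.

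**The concern.** The primary objective compares the intervention with usual care at 6 months. Whether a participant takes up an outside programme or a weight-loss drug is decided after randomisation, and it plausibly relates both to how the participant is doing and to the later CAP. If that event ends follow-up, the outcome is missing for a reason linked to its value. The remaining participants are then no longer the groups that were randomised.

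The decision is also discretionary in an open-label trial. Section 7.2 gives no criterion for when a barred start should lead to withdrawal, so similar cases can be handled differently. The loss is avoidable, because the 6-month VCTE is already scheduled in both arms (Section 1.3, Tables 1 and 2).

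**Working it through.** **Tracing the rules.** Take a participant who starts a barred programme at month 3.

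1. Section 5.3 applies in both arms, so the start is disallowed.
2. Section 7.2 permits withdrawal from the study, either as a disallowed therapy or programme or, for a structured programme or weight-loss drug, arguably as a newly met exclusion 6 or 7.
3. For a wait-list control, the intervention begins only after Visit 2 (Section 4.1; Table 2). Section 7.1 is worded around discontinuing the intervention, so it does not clearly apply. Nothing else calls for a CAP measurement after withdrawal.
4. For an intervention participant, Section 7.1 may prompt a VCTE when the intervention stops. A scan at month 3 is not the 6-month value, and withdrawal from the study ends the visits at which that value would be obtained.
5. Section 9.3.2 does not say how a missing 6-month CAP is counted.

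The 6-month CAP can therefore be lost in either arm.

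**Size.** The plan has no figure for this event. Section 9.2 allows up to 20% dropout (60 × 0.80 = 48 evaluable per arm) without dividing it by cause, and states no responder rates. What follows is illustration under assumed inputs.

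If k of 60 controls start a programme and are dropped, the observed control response rate differs from the as-randomised rate by

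shift = (k/60) × (starters' rate − other controls' rate).

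Assume k = 1 to 3, other controls responding at 20%, and starters at 20-60%:

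- k = 1: (1/60) × (0 to 40 points) = 0 to 0.7 points
- k = 3: (3/60) × (0 to 40 points) = 0 to 2.0 points

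For scale, the standard error of the between-arm difference with 60 per arm and 20% response in both is √(2 × 0.20 × 0.80 / 60) = √0.00533 = 7.3 points. The largest shift above is 2.0/7.3 = 0.27 of one standard error.

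**Direction.** Dropping starters changes the estimated difference (intervention minus control) by

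(kC/60) × (starter − other rate, control) − (kI/60) × (starter − other rate, intervention),

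where kC and kI are the numbers dropped in each arm. The documents give none of these four quantities. Equal losses with equal rate gaps cancel. If starters are mainly people doing poorly, the signs reverse.

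**The case against.** The strongest reply is that barring outside programmes is reasonable in a pilot, that withdrawal is only permitted and not required, and that outside treatment contaminates the pre-post analysis in Section 4.2. Section 9.1 also frames the primary hypothesis around those who complete the intervention. Section 10.1.7 already has non-compliance documented, and Section 2.2 describes uptake of lifestyle change as very limited. All of this supports keeping the bar and expecting a small effect. It does not support ending follow-up: the contamination can be handled by an analysis without these participants, whereas a scan that was never taken cannot be recovered.

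A reader might infer more than the text supports, in three ways.

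- *That the rules treat the arms differently.* Section 7.2 also says "Subjects who sign the informed consent form and are randomized but do not receive the study intervention may be replaced", and Section 9.3.2 leaves out those who never provided FitBit data. Neither rule is triggered by starting a programme; on such a reading they would reach a control who left early for any reason. Table 2 also marks the FitBit row at Visit 1 for wait-list participants. These are separate questions.
- *That the bar conflicts with usual care.* Section 4.1 says controls follow usual care, and Section 6.1.1 includes brief lifestyle advice and occasional nutritionist referral in it. Read together, these already allow such care.
- *That the bias is large.* With k = 1 to 3 unknown outcomes, the control rate is undetermined over k/60, or 1.7 to 5.0 points. That is the width of an all-or-none bound and not a bias. Reaching 8 points needs 20% of controls to start a programme and a 40-point gap (0.20 × 40), which sits poorly with Section 2.2.

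**Conclusion.** The point holds as a gap in the withdrawal rule. Sections 5.3 and 7.2 together let a barred start end study follow-up with only the reason recorded, and Section 7.1 does not clearly protect a wait-list control in months 0-6. The exposure exists in both arms. Its size and direction cannot be derived from the documents. It is probably small: 0 to 2.0 points on the control rate for up to 3 of 60 withdrawn controls, under assumed response rates that also presume starters do no worse than others. No stated figure in the plan is contradicted. This is a cheap improvement to the design and not a fault that would by itself overturn the result.

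**What to change.** - **Section 5.3:** keep the bar.
- **Section 7.2:** make starting a disallowed therapy or programme a documented deviation, and at most a reason to stop the study intervention, not a reason to end study follow-up. Apply the same to the ground for newly met exclusion criteria where the criterion is exclusion 6 or 7; otherwise the same participants could still be withdrawn by that route. The other grounds, and the participant's own right to withdraw, are unchanged.
- **Follow-up:** obtain the scheduled 6-month VCTE with CAP from these participants in both arms.
- **Section 9.3.2:** analyse them as randomised in the primary comparison, and repeat the between-arm and pre-post analyses without them as a sensitivity analysis. The deviation record identifies them.

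The cost is a few sentences; no visit or scan is added to the schedule. The estimated effect may be somewhat smaller, because controls who took up other treatment stay in. As an illustration with 48 per arm, 45% response on intervention and 20% in other controls, suppose 5% of controls start a programme and respond at 60%. The control rate is then 0.95 × 20% + 0.05 × 60% = 22%, and power is 67% with them kept against 74% with them withdrawn. The gain is a comparison of the groups as randomised, not more power.

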5.4 SCREEN FAILURES

Screen failures are defined as participants who consent to participate in the clinical trial but are not subsequently randomly assigned to the study intervention or entered in the study. A minimal set of screen failure information is required to ensure transparent reporting of screen failure participants, to meet the Consolidated Standards of Reporting Trials (CONSORT) publishing requirements and to respond to queries from regulatory authorities. Minimal information includes demography, screen failure details, eligibility criteria.

Individuals who do not meet the criteria for participation in this trial (screen failure) because of a lack of biopsy or imaging evidence of NAFLD within the designated time frame may be rescreened. Rescreened participants should be assigned the same participant number as for the initial screening.

5.5 STRATEGIES FOR RECRUITMENT AND RETENTION

Potential participants will be identified through Data Direct, EMERSE or via screening of patients with NASH/NAFLD in our general hepatology clinics. Eligible participants will be recruited via phone, text or from our general hepatology clinics at the time of a routinely scheduled outpatient clinic appointment. Individuals who complete the entire study will receive \$75, with \$25 provided after the completion of each study visit and associated data collection for that visit.

6 STUDY INTERVENTION(S) OR EXPERIMENTAL MANIPULATION(S)

6.1 STUDY INTERVENTION(S)

6.1.1 STUDY INTERVENTION OR EXPERIMENTAL MANIPULATION DESCRIPTION

This is a randomized trial comparing a structured mobile technology-based lifestyle intervention compared to usual care.

Intervention

-Education: Patients in the intervention arm will receive our NAFLD educational folder with an overview of contents by study staff. The folder includes: 1) NAFLD disease information including diagnosis, clinical manifestations, natural history and treatments; 2) NAFLD nutritional recommendations including sample menus; 3) NAFLD physical activity recommendations including walking programs and physical activity logs; 4) weight tracking logs; and 5) resources for diet and exercise programs.

-**Physical Activity**: All participants in the intervention arm (N=60) will receive a FitBit Zip for monitoring of step counts. The Fitbit wirelessly syncs data from the tracker to the Fitbit software or app. Study staff will assist with downloading the software and will instruct participants to wear their FitBit during waking hours every day. At any time if the participant has questions or problems regarding the use of the FitBit, a study staff member can be contacted. Study staff will retrieve users' step count data for analysis weekly and will provide subject with personalized feedback on physical activity with tailored step count goals (10% increase per week with max increase 800 steps per week to a maximum of 10,000 steps/week) and motivational messaging via e-mail. Patients with consecutive days without data recorded or with other signs of low FitBit usage (days with minimal step counts) will be contacted by study staff via e-mail or phone if necessary to encourage use. Feedback will occur weekly for the first 3 months of the intervention and then transition to biweekly for the last 3 months. Participants will also complete the short-version IPAQ for physical activity at enrollment, 6 month and 12 month follow-up visits.

-Nutrition: Patients in the intervention arm will have a nutritional assessment by a GI nutritionist specializing in NAFLD either at the enrollment visit if time allows, or in a separate in person or phone assessment within the first 2 weeks of enrollment. All patients will also complete the "Starting the Conversation" nutritional questionnaire for patients with metabolic disease at enrollment, 6 month and 12 month follow-up visits.(15)

Usual Care

At our center, patients with NAFLD /NASH without decompensated cirrhosis are seen every 6-12 months. Visits are approximately 15-20 minutes and consist of review of BMI/weight, recent hepatic panel and Fibroscan if ordered. Management typically consists of a breif overview of lifestyle changes including improvements in nutrition and physical actiity. Vitamin E is prescribed In a small proportion of patients. A similarly small proportion of patients are formally referred to and subsequently evaluated by a nutritionist.

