3 OBJECTIVES AND ENDPOINTS

OBJECTIVES	ENDPOINTS	JUSTIFICATION FOR ENDPOINTS
Primary		
Compare the effectiveness of usual care to a mobile technology based lifestyle intervention on change in liver and metabolic related parameters.	Reduction in amount of hepatic steatosis (≥5% overall reduction in CAP score) at 6 months.	Hepatic steatosis is a liver specific outcome that has been shown to improve with diet and exercise and is associated with risk of downstream clinical outcome such as development of NASH and cirrhosis.
Secondary		

OBJECTIVES	ENDPOINTS	JUSTIFICATION FOR ENDPOINTS
Improvements in other liver-specific and metabolic outcomes	weight loss, increase in total physical activity (based on step counts)	Weight loss has been associated with histologic improvements in NAFLD and NASH. Physical activity has been shown to improve fibrosis, liver enzymes, metabolic parameters and HRQOL.

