4 STUDY DESIGN

4.1 OVERALL DESIGN

This randomized clinical pilot trial will compare a mobile technology-based lifestyle intervention to a waitlist control group receiving usual care for adult patients with NAFLD. The intervention will use FitBit to track and promote physical activity through tailored longitudinal feedback. Patient will also receive nutritional counseling with serial nutritional assessments. The primary endpoint will be change in amount of hepatic steatosis. Secondary outcomes include changes in weight and physical activity (assessed by trend in step counts). A wait-list control design will be applied. 60 Patients will be randomized to the intervention arm for 6 months and 60 to usual care (the wait-list control). Those initially randomized to the intervention arm will then transition to a 6-month post intervention monitoring period to assess maintenance of behavior change and sustainability of impact on outcomes of interest. Individuals initially randomized to usual care, will transition to the intervention at month 6 for a total of 6 months.

The intervention arm will receive tailored physical activity and nutritional counseling, and the waitlist control arm which will follow usual and customary care for NAFLD patients attending our Heptology clinic for 6 months and then receive the 6-month intervention.

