6.4 STUDY INTERVENTION/EXPERIMENTAL MANIPULATION ADHERENCE

Adherence will be assessed by the following:

-Completion of all study visits and data collection elements

-Percentage of days with valid FitBit data (>300 steps per day as defined in behavioral health literature). Step count data will be assessed weekly for each participant.

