9.3.3 ANALYSIS OF THE SECONDARY ENDPOINT(S)

Analysis of secondary endpoints are not dependent on findings of primary endpoint.

-% weight loss: at month 6

-Physical activity: ≥10% increase in total minutes/week of physical activity based on IPAQ at month 6

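### Section 6.1.1 states the step-goal ceiling per week (1,429 steps/day), so on its natural reading a participant already at that level gets a flat or lower goal

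*Combined protocol and SAP*

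**What the plan says.** Section 6.1.1 (Physical Activity) describes weekly retrieval of step counts and personalized goals set by this rule: "10% increase per week with max increase 800 steps per week to a maximum of 10,000 steps/week". The same paragraph says that staff will "instruct participants to wear their FitBit during waking hours every day", and sets the contact schedule: "Feedback will occur weekly for the first 3 months of the intervention and then transition to biweekly for the last 3 months".

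Section 4.1 gives the purpose: "The intervention will use FitBit to track and promote physical activity through tailored longitudinal feedback". Section 4.3 cites an activity target of at least 150 minutes a week at moderate intensity. The only other step figure is the wear criterion in Section 6.4, which is per day: "Percentage of days with valid FitBit data (>300 steps per day as defined in behavioral health literature".

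The activity endpoint appears in two forms. Section 3 has "increase in total physical activity (based on step counts", and Section 4.1 likewise refers to the trend in step counts. Section 9.3.3 uses an "increase in total minutes/week of physical activity based on IPAQ at month 6".

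No section restates the ceiling per day, corrects it, or reports baseline step counts.

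**The concern.** The rule sets the dose of the physical-activity component. It applies to the 60 participants in the intervention arm during the randomized 6 months, and to wait-list participants when they start the intervention at month 6. A weekly ceiling of 10,000 steps, spread over seven days of wear, is a low daily figure. Applied literally as a limit on the goal, it stops or reverses goal-setting for anyone already walking that much.

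The stake is the strength and reproducibility of the intervention. Staff who follow the text would weaken it for such participants. Staff who use a daily goal instead would depart from the written protocol, and another team could not reconstruct the delivered rule from this document. Any effect on the activity endpoint is direct where it is measured by step counts (Sections 3 and 4.1) and indirect where it is measured by IPAQ minutes (Section 9.3.3).

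**Working it through.** **Inputs (Section 6.1.1).** Rate 10% per week; increment limit 800; ceiling 10,000 steps/week; wear on 7 days a week. The plan derives no figure from these, so there is none to reproduce.

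**1. Ceiling per day.** 10,000 / 7 = 1,428.6, or 1,429 steps/day.

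**2. Ceiling applied to the goal.** Next goal = min(current + min(0.10 × current, 800), 10,000), in weekly totals. The baselines below are assumptions chosen to show a range.

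| Assumed baseline, steps/day | Weekly total | First goal, steps/week | Change |
|---|---|---|---|
| 1,000 | 7,000 | 7,700 | +10.0% |
| 1,300 | 9,100 | 9,900 | +8.8% |
| 2,000 | 14,000 | 10,000 | −28.6% |
| 3,000 | 21,000 | 10,000 | −52.4% |
| 5,000 | 35,000 | 10,000 | −71.4% |
| 7,500 | 52,500 | 10,000 | −81.0% |

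At exactly 10,000 steps/week the goal is flat. Below that it rises but soon stops: 1,000 steps/day reaches the ceiling after 4 weekly increments, and 1,300 after 2.

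**3. Ceiling applied to the cumulative increase.** The final goal is at most baseline + 10,000 steps/week. Everyone's goal rises, by no more than 10,000 / 7 = 1,429 steps/day over the whole intervention.

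**4. The 800-step limit.** Here a week may be the unit or the updating interval.
- On a weekly total: 800 / 7 = 114 steps/day.
- On a daily goal, updated weekly: 800 steps/day, or 800 × 7 = 5,600 steps/week.

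The two differ by a factor of 7. Pairing an 800 steps/day limit with the written ceiling on the goal would make the limit idle, because 10% of 1,429 is only 143. The two units therefore need settling together.

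**5. Probable intended ceiling.** Three things point to a daily figure: the aim of promoting activity (Section 4.1), the 150-minute target (Section 4.3) and the per-day wear criterion (Section 6.4). On the second, 10,000 / 150 = 67 steps/min. If the target were met by walking, any faster cadence would pass the weekly ceiling in those minutes alone. The documents give no cadence, so this supports the inference without proving it.

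**6. Rule on daily figures.** With a ceiling of 10,000 steps/day (70,000/week) and the 800 limit on the daily goal, assumed baselines of 2,000, 3,000, 5,000 and 7,500 steps/day reach the ceiling after 18, 13, 8 and 4 weekly increments. Everyone below 10,000 steps/day gets a rising goal.

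**The case against.** The best defence is that trained staff would not apply the rule in a self-defeating way. Its first element is an increase, the goals are tailored, and Section 6.2.1 says that staff are trained on step-count goals and had shown proficiency in standard procedures. This stands as a caution: the documents do not show that any participant received a lowered goal, and a reader should not infer it. It does not repair the text, because Section 6.2.1 gives no alternative rule.

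A second defence is that 10,000 may limit the cumulative increase. That is the less natural reading, but not an absurd one: 10,000 / 800 = 12.5 increments, close to the number of weekly contacts in the first 3 months. On that reading no goal is flat or lower at 1,429 steps/day, so that consequence belongs to the natural reading alone. What remains is a small total rise and an unclear line.

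A reader might also infer that the three numbers themselves reveal a daily intent, because the 800 limit overrides the 10% rate above 800 / 0.10 = 8,000, just under 10,000. That does not follow. The relation is identical in weekly units, and preferring the daily version needs a view of realistic step counts that the documents do not supply.

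Finally, the stakes are limited. The primary endpoint is CAP, and Section 9.3.3 measures activity by IPAQ. This stands, and it bounds the importance of the point.

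**Conclusion.** The line is wrong as written, with minor to moderate importance. As the only statement of the rule, it sets a ceiling of 1,429 steps/day. With the maximum applied to the goal, it gives a flat or lower goal to anyone at or above that level, against the 10% rise and the purpose in Section 4.1. With the maximum applied to the cumulative increase, goals rise by at most 1,429 steps/day in total.

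A daily ceiling written as weekly is the probable explanation, but it is an inference from the purpose, the activity target and the per-day wear criterion. The unit of the 800-step limit is open, and a reader should not treat 800 steps/day as established.

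How many participants are affected cannot be stated. Sample size, power, alpha and the primary CAP analysis do not change.

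**What to change.** The investigators should confirm both units and correct the line. The most probable wording is: *daily-average step goal increased by 10% per week, to a maximum of 10,000 steps/day*, with two additions:

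- whether the 800-step limit applies to the daily goal (5,600 steps/week) or to the weekly total (about 114 steps/day);
- that no goal is set below the participant's current activity.

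If weekly totals are preferred, the equivalent ceiling is 70,000 steps/week. The feedback template and staff training should then be checked against the corrected rule.

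The cost is a one-line amendment and that check. The unit of the 800-step limit is a real choice, because the two options differ sevenfold in the permitted rise. Whether goals should rise only at the biweekly contacts in the last 3 months is a separate question and not part of this correction.
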